Based on literature from compounds with similar mechanism of action of PDR001, instructions have been developed regarding how to identify, assess severity and manage irAEs that may occur in patients receiving PDR001. The dose modification requirements and AE management guidelines for the potential irAEs are provided in the following tables: diarrhea/colitis ([Table 6-2](#)), hepatitis (liver laboratory alterations) ([Table 6-3](#)), skin (rash) ([Table 6-4](#)), nephritis ([Table 6-5](#)), pneumonitis ([Table 6-6](#)), encephalitis ([Table 6-7](#)), endocrinopathies ([Table 6-8](#)), PDR001-infusion reaction & cytokine release syndrome ([Table 6-9](#)), and other potential immune-related AEs of special interest ([Table 6-10](#)). Any grade 4 irAE must result in permanent discontinuation of PDR001.

Under the category of OTHERS ([Table 6-11](#) and [Table 6-12](#)) are included several irAE of interest that must be managed specifically and for which not specific guidance are provided in the table below. OTHERS include (but is not restricted to) the following events: autoimmune neuropathy, demyelinating polyneuropathy, Guillain-Barre, myasthenia Gravis-like syndrome, non-infectious myocarditis, non-infectious pericarditis, pancreatitis and rapid onset of grade 3 fatigue in the absence of disease progression.

Patients receiving PDR001 may experience irAEs other than those listed in this document; therefore, all AEs of unknown etiology associated with drug exposure should be evaluated to determine if they are possibly immune-related. In cases where the specific irAEs are not listed in the tables below, the investigator should follow the dose modification requirements in [Section 6.3.1.3](#) which details the measures to be taken for suspected (they could be potentially immune-related or non-immune-related) AEs. Investigators are encouraged to contact the sponsor as needed to discuss cases that warrant separate discussion outside of the scope of the current instructions.

The dosing modification requirements are mandatory; however, the AE management guidelines are recommendations and can be modified according to local practices. The management of irAEs may include initiation of antibiotics for prophylaxis against opportunistic infections.

Table 6-2 Mandatory dose modification requirements and recommended clinical management guidelines for potential immune-related diarrhea/colitis

Diarrhea/Colitis (NCI-CTCAE v4.03)		

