Grade	Recommended Adverse Event management guidelines	Mandatory Dose Modification requirements
Grade 1 (< 4 bowel actions per day over baseline) mild Grade 2 (4-6 bowel actions per day over baseline) and / or abdominal pain/ blood in stool.	
 ● Diet ● Hydration ● Loperamide: initially 4 mg, followed by 2 mg every four hours or after every unformed stool; maximum 16 mg/day. Continue until diarrhea free for 12 hours; ● Diarrhea > 24h: loperamide 2 mg every two hours; maximum 16 mg/day. Consider adding oral antibiotics. ● Diarrhea > 48hrs: loperamide 2 mg every two hours; maximum 16 mg/day. Consider other second-line therapies for diarrhea (e.g: (octreotide, oral diphenoxylate) and oral antibiotics ● If Grade 2 and no improvement in 5 days may require oral steroids ● If Grade 2 diarrhea persists >1 week consider GI consultation and endoscopy to evaluate for colitis. ● If Grade 2 persists for 5 days and worsening of symptoms or diffuse ulcerations and bleeding seen on endoscopy, commence steroids at a dose of 0.5-1mg/kg per day of prednisolone (or IV equivalent) and continue until symptoms improve to Grade 1. If no improvement occurs, manage as per Grade 3. Steroids can be tapered as per Section 6.3.1.2.2. ● Sigmoidoscopy and biopsy can be considered and may assist in determining the duration of steroid taper based on the evidence of macroscopic and microscopic inflammation. 	
 ● Continue PDR001 treatment ● If diarrhea is Grade 2, despite loperamide at 2 mg every two hours for > 48hrs: 
 ● Interrupt PDR001 until diarrhea recovers to Grade ≤1 and then restart PDR001 treatment at the same dose and schedule.

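### Mandatory PDR001 hold for Grade 2 diarrhea/colitis: the loperamide trigger is ambiguous under the row's own 16 mg/day maximum and unmet under alternatives the protocol allows

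*Protocol*

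**What the plan says.** Table 6-2 in Protocol Section 6.3.1.2.1 has a recommended-management column and a mandatory dose-modification column. The text above it gives them different force: "The dosing modification requirements are mandatory; however, the AE management guidelines are recommendations and can be modified according to local practices".

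In the Grade 1-2 row, the recommended column sets out loperamide in three steps:

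- Initial: "Loperamide: initially 4 mg, followed by 2 mg every four hours or after every unformed stool; maximum 16 mg/day".
- After a day: "Diarrhea > 24h: loperamide 2 mg every two hours; maximum 16 mg/day".
- After two days: "Diarrhea > 48hrs: loperamide 2 mg every two hours; maximum 16 mg/day". At this step sites are also told to consider second-line agents, with octreotide and diphenoxylate as examples.

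The mandatory column starts from an instruction to carry on with PDR001. It departs from that on one condition: "If diarrhea is Grade 2, despite loperamide at 2 mg every two hours for > 48hrs". When the condition is met, the action is: "Interrupt PDR001 until diarrhea recovers to Grade ≤1 and then restart PDR001 treatment at the same dose and schedule". The mandatory cell gives no daily maximum and mentions no antidiarrheal other than loperamide.

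**The concern.** A mandatory safety rule should be one that a site can apply, and a monitor can check, from its own wording. This one has two weaknesses.

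First, the schedule it names does not fit the daily maximum in the neighboring cell if it is given day and night. The mandatory cell is silent on which of the two governs.

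Second, the condition is defined by one regimen from a column that sites may change. A site that treats persistent Grade 2 diarrhea with something else follows the protocol, yet never reaches the written condition for the hold.

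At stake is whether PDR001 must be held in persistent Grade 2 diarrhea or colitis, a category that in this row includes abdominal pain or blood in the stool. Diarrhea/colitis is an adverse event of special interest (Section 8.1.3). There is also a knock-on effect. Section 6.3.1.1 starts the 12-week discontinuation clock when an immune-related event reaches a grade requiring interruption. Here interruption depends on grade plus a drug condition, so an unclear trigger leaves the start of that clock unclear too.

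**Working it through.** **Inputs**, all from the Grade 1-2 row of Table 6-2: single dose 2 mg; interval 2 h; daily maximum 16 mg; trigger duration more than 48 h.

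**1. Schedule given round the clock**

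- Doses per day: 24 h / 2 h = 12.
- Daily amount: 12 × 2 mg = 24 mg, against 16 mg allowed.
- Excess: 24 − 16 = 8 mg/day; 8 / 16 = 50%.
- Over 48 h: 2 × 24 = 48 mg, against 2 × 16 = 32 mg.

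Uninterrupted two-hourly dosing therefore does not reproduce the 16 mg/day figure.

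**2. Schedule given up to the maximum**

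- Doses per day: 16 mg / 2 mg = 8.
- The eighth dose falls at (8 − 1) × 2 h = hour 14. With its interval it covers 8 × 2 h = 16 of 24 h.
- Spread evenly over the day, 8 doses mean one every 24 / 8 = 3 h.

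This reading does reproduce 16 mg/day. Under it, a patient can be on the regimen for more than 48 h and meet the trigger.

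**3. The initial step, for comparison**

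On day 1, 4 mg followed by 2 mg at hours 4, 8, 12, 16 and 20 gives 4 + 5 × 2 = 14 mg, and later days give 6 × 2 = 12 mg. The clock-based part of that step fits within the maximum. The mismatch arises only with the two-hourly schedule, which is the one the mandatory trigger uses.

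**4. The trigger beside the row's own sequence**

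- The row starts two-hourly dosing once diarrhea has lasted more than 24 h. At 48 h of diarrhea, a patient following the row has been on the trigger schedule for at most about 48 − 24 = 24 h.
- At that point the row keeps loperamide but also suggests second-line agents. If these are added, the 48-hour count can continue. If they replace the two-hourly schedule, it stops short.
- A site that used a different antidiarrheal or interval from the outset, as Section 6.3.1.2.1 permits, never starts the count. Read as written, the mandatory cell then leaves the patient under its default instruction to continue.

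**5. Other tables**

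In Tables 6-3, 6-5, 6-6, 6-7 and 6-10, a Grade 2 event leads to interruption by its grade, without reference to a concomitant-drug schedule, so this question does not arise there. The comparison shows only where the difficulty lies, not which kind of rule is right.

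**The case against.** The strongest reply is that the row twice joins the two-hourly interval to the 16 mg/day maximum in one phrase. The trigger is then shorthand for that capped regimen, which can be given for more than 48 h. Moreover, the maximum appears only in the modifiable column, so it cannot make a mandatory condition unattainable. This stands. A reader might infer from the arithmetic that the hold can never be triggered. That would need both uninterrupted day-and-night dosing and a binding maximum, and the documents establish neither.

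A reader might also infer that no hold is required until Grade 3. Other text prevents that conclusion:

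- Section 6.4.3 bars the next PDR001 dose until steroids given for an immune-related event are below 10 mg/day of prednisone or equivalent.
- The same row brings in steroids for Grade 2 events that do not improve or that worsen over 5 days, and refers non-improving cases to Grade 3 management.
- Section 6.3.1.2.1 says in general terms that persistent lower-grade events usually call for interruption or discontinuation.
- Section 7.1.5 lets the investigator stop treatment.

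These protections are real but partial. Starting steroids is itself in the modifiable column, and the last two provisions are general or permissive. They do not settle when the mandatory Grade 2 hold applies.

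Exposure is also limited. PDR001 is given every 28 days with a 7-day window either side (Section 6.1.1), so the ambiguity matters only when a dose falls due during the episode. None of this answers the second weakness: reading the trigger as the capped regimen does nothing for a patient on an allowed alternative.

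**Conclusion.** The point holds as an ambiguity in a mandatory safety rule. The named schedule is 24 mg/day if continuous, against 16 mg/day beside it, and the mandatory cell does not say whether the capped regimen of up to 8 doses a day counts. Where an allowed alternative replaces that schedule, the written trigger is not met. The first part rests on reading the interval as round the clock; the second does not depend on the arithmetic.

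Two further inferences are not supported. One is that interruption rates would not be comparable across sites in a way that harms the analysis. The study is single-arm, and SAP Section 2.1 pools centers and assesses no center effect. The other is that the interim diarrhea rates in Section 1.2.1.2 (20.0% and 14.3%) size the problem. They are all-grade and any-cause, and the documents give no count of persistent Grade 2 immune-related events.

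No sample size, operating characteristic or efficacy result changes. Recruitment is closed, but Section 6.1.5 lets patients stay on treatment after the 10-Aug-2018 cut-off, so the table remains in use. It should be clarified.

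**What to change.** Two reconciliations in the Grade 1-2 row of Table 6-2:

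1. Reconcile the two-hourly loperamide schedule with the 16 mg/day maximum, wherever the two appear together.
2. Reconcile the mandatory trigger with the statement in Section 6.3.1.2.1 that the management column may be modified. The cell should say how the trigger applies to a patient on the capped regimen, and how it applies when another antidiarrheal regimen is used.

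The dose, the interval, the duration and the hold rule itself are for the sponsor's clinical team to set. The cost is wording in one table row, carried by a protocol amendment or a clarification to sites. No analysis needs to be rerun.

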8. Patient must have an Eastern Cooperative Oncology Group (ECOG) performance status 0-2.
9. Tumor biopsy material must be provided for all patients [REDACTED]:
- Well-differentiated (G1/2) NET: Biopsy material must be provided following the diagnosis of metastatic disease. The tumor sample must be collected from a metastatic site not previously irradiated and **should preferably be taken within 6 months but not more than 24 months prior to start of study treatment.**
- [REDACTED]

- Poorly-differentiated GEP-NEC: Biopsy material must be collected from the primary tumor or from a metastatic site not previously irradiated, **taken not more than 24 months prior to start of study treatment.**
10. Women of childbearing potential must have had a negative serum pregnancy test within 72 hours prior to the start of study treatment. Highly effective contraception must be used while on study.
 11. Patient is deemed by the investigator to have the ability and means to be compliant with the protocol (treatment and follow-up).
 12. Patient must meet the following laboratory values at the screening visit:
 - Absolute Neutrophil Count $\geq 1.5 \times 10^9/L$
 - Platelets $\geq 75 \times 10^9/L$
 - Hemoglobin (Hgb) ≥ 9 g/dL
 - Serum creatinine < 1.5 mg/dL
 - Total bilirubin ≤ 1.5 x ULN
 - Aspartate transaminase (AST) ≤ 3.0 x ULN, except for patients with liver metastasis, if AST ≤ 5.0 x ULN
 - Alanine transaminase (ALT) ≤ 3.0 x ULN, except for patients with liver metastasis, if ALT ≤ 5.0 x ULN

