Severity	Recommended Adverse Event management guidelines	Mandatory Dose Modification requirements
Grade 2: AST or ALT > 3x ULN to ≤ 5.0x ULN and/or bilirubin > 1.5x ULN to ≤ 3x ULN (if patient meets criteria for Hy's law, refer to Section 6.3.3.1)	Monitor hepatic laboratory tests more frequently (every 2-3 days) until returned to baseline values	
 Interrupt PDR001 treatment until recovery to Grade ≤1 or baseline** 
 Once recovered restart PDR001 treatment at the same dose and schedule
Grade 3 or 4: AST or ALT >5.0xULN and/or bilirubin > 3.0x ULN	
 Monitor hepatic laboratory tests more frequently (every 2-3 days) until returned to baseline values. Consider appropriate consultation* with hepatologist and liver biopsy to establish etiology of hepatic injury, if necessary If after 2-3 days new liver assessment shows worsening of laboratory test consider to initiate treatment with steroids prednisolone 1-2 mg/kg/day or IV equivalents. Add prophylactic antibiotics for opportunistic infections When symptoms improve to Grade ≤1, a steroid taper with dexamethasone 4 mg every 4 hours or prednisone at 1 to 2 mg/kg should be started and continued over no less than 4 weeks. If serum transaminase levels do not decrease 48 hours after initiation of systemic steroids, oral mycophenolate mofetil 500 mg every 12 hours may be given. Infliximab is not recommended due to its potential for hepatotoxicity 	Permanently discontinue PDR001**

* Send viral serology looking for hepatitis A, B, C & CMV and rule out any potential cause of liver injury (i.e. alcohol, other medications, etc.)

**For patients with liver metastasis who begin treatment with grade 2 AST or ALT, if AST or ALT increase by 2 times relative to baseline and last for at least 1 week then the patient should be discontinued

Note: For additional information on follow-up of potential drug induced liver injury cases, refer to [Section 6.3.3.1](#).

Table 6-4 Mandatory dose modification requirements and recommended clinical management guidelines for potential immune-related skin events

Rash Events (NCI-CTCAE v4.03)		
Grade	Recommended Adverse Event management guidelines	Mandatory Dose Modification requirements

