6.3.3.1 Follow up on potential drug-induced liver injury (DILI) cases

Patients with transaminase increase combined with TBIL increase may be indicative of potential DILI, and should be considered as clinically important events.

The threshold for potential DILI may depend on the patient's baseline AST/ALT and TBIL value; patients meeting any of the following criteria will require further follow-up as outlined below:

- For patients with normal ALT and AST and TBIL value at baseline: AST or ALT > 3.0 x ULN combined with TBIL > 2.0 x ULN
- For patients with elevated AST or ALT or TBIL value at baseline: [AST or ALT > 2 x baseline AND > 3.0 x ULN] OR [AST or ALT > 8.0 x ULN], combined with [TBIL > 2 x baseline AND > 2.0 x ULN]

Medical review needs to ensure that liver test elevations are not caused by cholestasis, defined as ALP elevation > 2.0 x ULN with R value < 2 in patients without bone metastasis, or elevation of ALP liver fraction in patients with bone metastasis.

Note: (The R value is calculated by dividing the ALT by the ALP, using multiples of the ULN for both values. It denotes whether the relative pattern of ALT and/or ALP elevation is due to cholestatic ($R \leq 2$), hepatocellular ($R \geq 5$), or mixed ($R > 2$ and < 5) liver injury).

In the absence of cholestasis, these patients should be immediately discontinued from study drug treatment, and repeat LFT testing as soon as possible, preferably within 48 hours from the awareness of the abnormal results. The evaluation should include laboratory tests, detailed history, physical assessment and the possibility of liver metastasis or new liver lesions, obstructions/compressions, etc.

1. Laboratory tests should include ALT, AST, albumin, creatine kinase, total bilirubin, direct and indirect bilirubin, GGT, prothrombin time (PT)/INR and alkaline phosphatase.
2. A detailed history, including relevant information, such as review of ethanol, concomitant medications, herbal remedies, supplement consumption, history of any pre-existing liver conditions or risk factors, should be collected.
3. Further testing for acute hepatitis A, B, C or E infection and liver imaging (e.g. biliary tract) may be warranted.
4. Obtain PK sample, as close as possible to last dose of study drug, if PK analysis is performed in the study.

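### For liver-metastasis patients who start at grade 2 AST/ALT, the grade 3/4 row of protocol Table 6-3 and its ** footnote set different PDR001 stopping criteria, and nothing says which governs

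*Protocol*

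**What the plan says.** **Entry.** Protocol Section 5.2, criterion 12, reads "Alanine transaminase (ALT) ≤ 3.0 x ULN, except for patients with liver metastasis, if ALT ≤ 5.0 x ULN". AST has the same allowance: "except for patients with liver metastasis, if AST ≤ 5.0 x ULN". Grade 2 in Table 6-3 is AST or ALT above 3 and up to 5 x ULN, so a patient with liver metastases may begin treatment at grade 2.

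**Grade 2 row of Table 6-3.** The mandatory action is "Interrupt PDR001 treatment until recovery to Grade ≤1 or baseline", and the cell carries the ** marker.

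**Grade 3/4 row of Table 6-3.** The trigger is "Grade 3 or 4: AST or ALT >5.0xULN and/or bilirubin > 3.0x ULN", with no duration condition. The mandatory action is "Permanently discontinue PDR001", also marked **.

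**Footnote **.** It names patients with liver metastasis who start at grade 2 AST or ALT and says "if AST or ALT increase by 2 times relative to baseline and last for at least 1 week then the patient should be discontinued". It does not mention bilirubin. It does not say whether it replaces the two marked cells or adds to them.

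**Section 6.3.1.2.1.** The dose modification column is mandatory, and the management column is advisory. Every grade 4 immune-related event has to end PDR001 permanently.

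**Section 6.3.3.1.** This covers AST/ALT elevation together with a bilirubin rise. With an elevated baseline, AST/ALT must be more than 2 x baseline and more than 3 x ULN, or else more than 8 x ULN. In addition, bilirubin must be more than 2 x its baseline and more than 2 x ULN. The action is: "In the absence of cholestasis, these patients should be immediately discontinued from study drug treatment". Table 6-3 points to this section for Hy's law cases and for follow-up of possible drug-induced liver injury.

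**The concern.** The row and the footnote are both in a mandatory table and apply to the same laboratory value in the same patient, yet they give different answers. A site that follows the row ends treatment for good. A site that follows the footnote does not yet have a reason to stop. Both could say that they followed the protocol.

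This affects patient safety and time on drug for people with liver metastases. It also affects adverse events leading to discontinuation, which SAP Section 2.8.1 tabulates and Section 2.2.1 repeats by subgroup. That count would partly reflect which reading each site took. No effect on the primary response-rate analysis is claimed.

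**Working it through.** **Inputs, all in multiples of ULN.** Baseline b lies in (3.0, 5.0] (Section 5.2 and the grade 2 definition in Table 6-3). The row stops at AST/ALT > 5.0. The footnote stops at 2 x b held for at least 1 week. The plan states no combined figure to reproduce.

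**Step 1: where the two criteria part.** Footnote threshold = 2 x b. For b in (3.0, 5.0] this lies in (6.0, 10.0], always above 5.0.

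| Baseline b | Row stops above | Footnote at 2 x b | Only the row is met | Footnote if read as 3 x b |
|---|---|---|---|---|
| 3.1 | 5.0 | 6.2 | above 5.0, below 6.2 | 9.3 |
| 4.0 | 5.0 | 8.0 | above 5.0, below 8.0 | 12.0 |
| 5.0 | 5.0 | 10.0 | above 5.0, below 10.0 | 15.0 |

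The last column treats the footnote's rise as an increase of two baselines on top of the first. The wording does not exclude this. However, Section 6.3.3.1 writes its parallel rule as a multiple of 2 x baseline, which favours the 2 x b column.

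**Step 2: the footnote adds to the row.** Since 2 x b > 5.0 for every eligible b, the row has already required permanent discontinuation before the footnote can be met. The footnote then has no effect.

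**Step 3: the footnote replaces the row.** Four things are then left open.

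- Above 5.0 and below 2 x b, the value is outside the grade 2 row and below the footnote, so no action is stated.
- At or above 2 x b, no action is stated during the 1-week wait.
- The row's separate trigger at bilirubin > 3.0 may or may not survive for this subgroup.
- SAP Table 5-3 puts grade 4 AST/ALT above 20 x ULN. With b at most 5.0, that is more than 20/5 = 4 x baseline, so the size condition is met on either reading of the multiple. The duration condition may not be. A grade 4 immune-related rise lasting under a week would end treatment under Section 6.3.1.2.1 but not under the footnote.

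**Step 4: worked cases.** Bilirubin baseline is taken as 0.8 x ULN, relation to PDR001 is suspected, and there is no cholestasis. These values are illustrative.

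| Baseline AST/ALT | Current AST/ALT | Bilirubin | Row | Footnote (2 x b) | Section 6.3.3.1 |
|---|---|---|---|---|---|
| 4.0 | 6.0 | 0.8 | met | not met (6.0/4.0 = 1.5) | not met |
| 4.0 | 8.5 | 0.8 | met at once | met only after 1 week (8.5/4.0 = 2.1) | not met |
| 4.0 | 8.5 | 2.5 | met at once | met only after 1 week | met, immediate stop |
| 4.5 | 8.5 | 2.5 | met | not met (8.5/4.5 = 1.9) | met through its > 8 limb |

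In the last two rows the bilirubin condition holds: 2.5/0.8 = 3.1 x baseline, and 2.5 > 2. On a grid of baselines 3.1 to 5.0 and ALT 3.1 to 24.9, Section 6.3.3.1 was never met with bilirubin at or below 2 x ULN.

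**The case against.** The strongest reply is that the marker itself settles the matter. The ** sits on the row's action and opens by naming a subgroup, so the natural reading is an exception for that subgroup, and Step 2 shows that the additive reading would leave it idle. I agree that this is the likelier intent. It turns a flat contradiction into an unstated precedence, but it does not fill the gaps in Step 3.

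A reader might infer that the protocol gives three stopping rules for one result, counting Section 6.3.3.1. The documents do not support that. The section needs a bilirubin rise as well and an absence of cholestasis, and Table 6-3 refers the combined pattern to it. What remains is narrower. In the combined pattern, an immediate stop and a 1-week condition both apply, and neither text says which prevails.

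A reader might also infer that a patient would be kept on drug for a week near 10 x ULN. Section 6.1.1 schedules one infusion every 28 days, so a 7-day wait covers a quarter of a cycle and often no dose falls due. Table 6-3 recommends liver tests every 2 to 3 days, and Section 7.1.5 lets the investigator stop treatment. The real difference is permanent stop against possible continuation.

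Finally, one could say that a trivial rise ends treatment: from 4.9 to 5.1 x ULN is 5.1/4.9 = 1.04, or 4%. That is a corner case. From 3.1, passing 5.0 takes a rise of about 61% (5.0/3.1 = 1.61). Section 6.3.1 also introduces these rules for events suspected to be related to PDR001, so a fluctuation put down to the metastases would not clearly trigger the row.

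Recruitment is complete at 116 patients, which limits the reach. It does not remove the problem, because Section 6.1.5 lets patients stay on treatment after 10-Aug-2018 and Section 7.1.7 leaves safety evaluations unchanged.

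**Conclusion.** The point holds for a suspected drug-related AST/ALT rise without a bilirubin rise, in patients with liver metastases who start above 3 and up to 5 x ULN. The row and the footnote diverge from just above 5 x ULN up to twice baseline (more than 6 and up to 10 x ULN), and during the 1-week wait above that. Neither reading of the footnote gives a complete rule. One makes it idle, and the other leaves gaps and conflicts with the grade 4 rule in Section 6.3.1.2.1.

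This rests on reading the footnote's multiple as 2 x baseline. Read as 3 x baseline, the threshold is more than 9 and up to 15 x ULN and the gap widens. The documents do not give the number of patients who started at grade 2 with liver metastases, so the effect on discontinuation counts cannot be sized. Only patients still on treatment could be affected from here on.

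**What to change.** The sponsor should reconcile the two marked rows of Table 6-3, footnote **, the grade 4 statement in Section 6.3.1.2.1 and Section 6.3.3.1 for this subgroup. The text should state:

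- for each cell marked **, whether the footnote replaces the cell or adds to it;
- the size of the rise as one multiple of baseline;
- what applies from 5 x ULN up to the footnote threshold, and during the 1-week wait;
- whether the row's bilirubin trigger still applies;
- which rule takes precedence for grade 4 events and when Section 6.3.3.1 is also met.

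Which threshold and duration apply is for the sponsor's clinical team, and no view is taken here.

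The cost is a wording change to one table footnote plus cross-references, made by protocol clarification or amendment. It needs no new data or procedures.
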